#### **1.3.5.1. Pharmacovigilance Activities**

Pharmacovigilance measures are in place and include adverse event collection from spontaneous, study, and literature sources, review of individual and aggregate reports, and ongoing signal management including signal detection and evaluation. Additional pharmacovigilance activities include targeted follow-up questionnaires for specific risks. In addition, the safety data from any ongoing and completed study will be reviewed. Any new safety findings discovered from any of these sources will be communicated in a timely fashion.

### **1.3.5.2. Risk Minimization**

Risk minimization activities are based on the communication of benefit risk information to physicians and patients, with the prescribing information as the main tool.

Additionally, there are targeted educational materials for physicians with an emphasis on the benefits and risks associated with the use of eltrombopag. The educational materials are updated as necessary to communicate the benefits and risks.

### **1.3.6. Conclusion**

Eltrombopag has been generally well tolerated in chronic ITP and HCV associated thrombocytopenia, in clinical studies for other indications under development, and in the post marketing setting.

The benefit risk profile of eltrombopag for the treatment of patients with chronic ITP and HCV associated thrombocytopenia to increase platelet counts and reduce or prevent bleeding or help achieve sustained viral response continues to be favorable. Additionally the benefit risk profile of eltrombopag for treatment in other indications under development, and in the post marketing setting continues to be favorable.

## **2. OBJECTIVE**

The objective of this study is to provide continuing treatment with eltrombopag for subjects who are currently participating in a Novartis sponsored investigational study of eltrombopag (parent study) and to collect long term safety data.

## **3. STUDY DESIGN**

This Phase IV, multicenter, non-randomized, open-label, uncontrolled, rollover study is designed to provide continued access to eltrombopag to eligible subjects. Enrollment into this study will be dependent upon the mutual agreement between Novartis and a site to participate in this study.

Subjects must provide written informed consent prior to any study-related assessment or procedure being performed or treatment with eltrombopag for this study. After informed consent is obtained, subjects must meet the eligibility criteria for this study in order to participate.

Protocol waivers or exemptions are not allowed with the exception of immediate safety concerns. Therefore, adherence to the study design requirements, including those specified in each Cohort section and the Time and Events Table [Appendix 1] are essential and required for study conduct.

The study will consist of a Transition Visit, Study Treatment Visits, and a Follow-Up Visit.

Safety will be evaluated through physical exams, clinical laboratory tests, and monitoring of adverse events as described in the Time and Events Table [Appendix 1] Additional safety assessments may be done as per standard of care (SOC) and or when medically indicated.

Assessment of clinical benefit will be performed throughout the study using local SOC as determined by the investigator to determine continued study participation and treatment with eltrombopag. Only subjects considered by the investigator to be receiving clinical benefit without unacceptable toxicity may continue on study treatment.

Subjects will receive a starting dose of eltrombopag at the same dose and administration that they were receiving at the time of their last study treatment visit in the parent study. Instructions for dose adjustments can be found in Section 5.4. Subjects may continue treatment in this rollover study until they are no longer receiving clinical benefit, develop an unacceptable toxicity, withdraw consent, enroll into another interventional study, or until another mechanism is available for the subject to receive eltrombopag such as compassionate use, named patient program, commercially available for the appropriate indication, etc. The duration of the study will be dependent on the length of time the subjects do not meet the protocol stopping criteria, but the study will end in 2023.

Refer to the Time and Events Table [Appendix 1] for timing of all assessments.

Supplementary study conduct information not mandated to be present in this protocol is provided in the accompanying Study Procedures Manual (SPM). The SPM will provide the site personnel with administrative and detailed technical information that does not impact subject safety.

### 3.1. Discussion of Design

The purpose of this study is to allow for continued treatment with eltrombopag in subjects who have participated in a Novartis sponsored investigational study with eltrombopag and met the protocol requirements for transitioning to the rollover study. Subjects participating in Investigator Sponsored Studies will not be eligible to participate in this study. Subjects will be closely monitored for stopping criteria. Subjects will follow the appropriate cohort (Section 3.2) based upon the indication and population of the parent study. The schedule of assessments and procedures to be performed during this study is provided in the Time and Events Table (Appendix 1). Subjects will continue to receive SOC therapies unless otherwise stated in the protocol.

The end of study is defined as the last subject, last visit.

The eltrombopag dose allowed in this study will be individualized based upon the dose/regimen received in the parent study at the time of transition to the rollover study. Optimal dosing of eltrombopag is based on platelet count in individual subjects.

Treatment with eltrombopag may enable subjects to initiate and maintain the dose and schedule of disease-modifying therapy. Disease modifying treatments (e.g. chemotherapy, azacitidine, decitabine and lenalidomide) will be allowed. Supportive SOC will be allowed as indicated by local practice throughout the study.

All subjects will receive eltrombopag at the dose that they were receiving at the time of the Transition Visit, except in the case where the subject required a dose modification in the parent study. If the dose was modified at the last study visit in the parent study, the subject will enter the rollover study and continue treatment on the modified dose, and the visit schedule at entry into the rollover study may be weekly to enable proper monitoring following the adjusted dose (Figure 1). However, if during the rollover study the investigator considers it appropriate to modify the dose of eltrombopag, the dose may be modified as needed based on guidelines in Section 5.4. **Dosage must never exceed the maximum dose allowed by the parent study.**

Each subject's visit schedule may begin at any point of the visit schedule in Figure 1 depending on the stability of their dose. Any time a change in dose is required, the subjects must return for weekly visits and progress through the visit schedule as detailed below.

### 3.2. Cohorts

#### 3.2.1. Cohort A (MDS/AML Adult Subjects)

Cohort A will consist of adult subjects who have completed study treatment with eltrombopag during their participation in a parent study for MDS/AML (i.e. TRC114968/ASPIRE).

#### 3.2.2. Cohort B (ITP Adult Subjects)

Cohort B will consist of adult subjects who have completed study treatment with eltrombopag during their participation in a parent study for ITP (i.e. TRA105325/EXTEND).

#### 3.2.3. Cohort C (ITP Pediatric Subjects)

Cohort C will consist of pediatric subjects who have completed study treatment with eltrombopag during their participation in a parent study for ITP. Once a subject turns 18 years of age, they may remain in the study and follow the Cohort B guidelines.

#### 3.2.4. Visit Schedule for Cohort A, Cohort B, and Cohort C

**Figure 1 Visit Schedule**

1. For Cohort B and Cohort C, more frequent visits may be required (Section 5.4.2.3.)

Subjects in **Cohort A, Cohort B and Cohort C** will complete the Transition Visit assessments (Section 8.1.) and then return for their next scheduled visit in 2 weeks, or

sooner if the visit schedule in the parent study had been more frequent than every two weeks (e.g. weekly schedule). Subjects who have been on a stable dose of eltrombopag for the previous 2 every two week visits may decrease the frequency of visits to once monthly visits. Subjects who are stable on a monthly dose for the previous 3 monthly visits may decrease the frequency of visits to once every 2 months. If any change in the study treatment dose is required, the schedule of visits must begin again with weekly visits for at least 4 weeks, followed by biweekly, then monthly and then bimonthly visits (See schematic in Figure 1).

Once treatment with eltrombopag is permanently discontinued, the subject will attend the follow up visit as per Appendix 1. If there are any uncertainties about the dose(s) of study treatment(s) to be administered or the visit schedule, the Novartis Medical Lead should be consulted.

## **4. SUBJECT SELECTION AND DISCONTINUATION/ COMPLETION CRITERIA**

### **4.1. Subject Selection Criteria**

#### **4.1.1. Number of Subjects**

Approximately 100 subjects will be transitioned to this study from other eltrombopag studies.

#### **4.1.2. Inclusion Criteria**

Specific information regarding warnings, precautions, contraindications, adverse events, and other pertinent information on eltrombopag or other approved agent(s) that may impact subject eligibility is provided in the Investigators Brochure (IB) for eltrombopag [GlaxoSmithKline Document Number UM2005/00217/08].

Deviations from inclusion criteria are not allowed because they can potentially jeopardize the scientific integrity of the study, regulatory acceptability or subject safety. Therefore, adherence to the criteria as specified in the protocol is essential.

Subjects eligible for enrolment in the study must meet all of the following criteria:

1. Written informed consent has been obtained from the subject (or subject's legally acceptable representative) prior to performance of any study-specific procedure.
2. The subject is participating in a Novartis sponsored investigational study of eltrombopag (parent study) within the past 28 days and is receiving clinical benefit without unacceptable toxicity as determined by the investigator.
3. Subjects with a QTc <450msec or <480msec for subjects with bundle branch block

The QTc is the QT interval corrected for heart rate according to either Bazett's formula (QTcB), Fridericia's formula (QTcF) or another method, machine or manual overread.

For subject eligibility and withdrawal QTcF will be used.

For purposes of data analysis, QTcF will be used.

The QTc should be based on single or averaged QTc values of triplicate electrocardiograms (ECGs) obtained over a brief recording period.

4. Women must be either of non-child bearing potential (see Section 8.4.8.1, for definition) or women with child-bearing potential and men with reproductive potential must be willing to practice acceptable methods of birth control during the study (See Section 8.4.8.1 for acceptable methods of birth control).
5. Women of childbearing potential must have a negative serum pregnancy test within 14 days of the first dose of study treatment and agree to use effective contraception, as defined in Section 8.4.8.1 during the study and for 4 weeks following the last dose of study treatment.
6. Men with a female partner of childbearing potential must have either had a prior vasectomy or agree to use effective contraception as described in Section 6.1 from time of first dose until 16 weeks after the last dose of study treatment.
7. In France, a subject will be eligible for inclusion in this study only if either affiliated to, or a beneficiary of, a social security category.

#### **4.1.3. Exclusion Criteria**

Deviations from exclusion criteria are not allowed because they can potentially jeopardize the scientific integrity of the study, regulatory acceptability or subject safety. Therefore, adherence to the criteria as specified in the protocol is essential.

Subjects meeting any of the following criteria must not be enrolled in the study:

1. Permanent discontinuation of eltrombopag in the parent study based upon the study treatment discontinuation or study withdrawal criteria from the parent study. Subjects who permanently discontinued treatment because they completed all study related treatments remain eligible.
2. The subject is pregnant or a lactating female.
3. Any serious and/or unstable pre-existing medical, psychiatric disorder or other conditions at the time of transition to this study that could interfere with subject's safety, obtaining informed consent or compliance with the study procedures, in the opinion of the investigator or Novartis Medical Lead.
4. **French subjects:** the French subject has participated in any study using an investigational drug during the previous 30 days, with the exception of eltrombopag, in the parent study.

## 4.2. Permanent Discontinuation from Study Treatment and Subject Completion Criteria

### 4.2.1. Permanent Discontinuation from Study Treatment

Subjects will receive study treatment until **no longer receiving clinical benefit as determined by the investigator**, death, or unacceptable adverse event, including meeting stopping criteria for liver chemistry defined in Section 5.10.1. In addition, study treatment must be permanently discontinued for any of the following reasons:

- Subject has taken or plans to take any other investigational product(s) during the study
- Subject becomes pregnant
- Significant deviation from the protocol
- Investigator's discretion
- Request of the subject or proxy (withdrawal of consent by the subject)
- Subject has an adverse experience that would, in the investigator's or Sponsor's judgment, make continued participation in the study an unacceptable risk
- Subject meets any of the liver chemistry threshold criteria (Section 5.10.2.)
- Another mechanism is available for the patient to receive eltrombopag such as eltrombopag receives regulatory approval and is commercially available and a reimbursement decision has been made in the patient's country, compassionate use, or a named patient program
- Subject is lost to follow-up
- Study is closed or terminated
- Subject has a QTc  $\geq 500$  msec (if baseline  $< 450$  msec), or QTc  $> 530$  msec (if baseline QTc 450-480 msec) or uncorrected QT  $> 600$  msec

The primary reason study treatment was permanently discontinued must be documented in the subject's medical records and electronic case report form (eCRF).

If the subject voluntarily discontinues from treatment due to toxicity, 'adverse event' will be recorded as the primary reason for permanent discontinuation on the CRF.

Once a subject has permanently discontinued from study treatment, the subject will not be allowed to be retreated.

Investigators will make an attempt to contact those patients who do not return for scheduled visits (e.g. by phone contact or certified letters).

All subjects who discontinue from study treatment will have safety assessments at the time of discontinuation and during post study treatment follow-up as specified in Time and Events Table [Appendix 1] and Section 8.3.

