### **5.10.2. Liver Chemistry Monitoring Criteria**

For subjects with ALT  $\geq 3$ xULN **but**  $< 5$ xULN **and** bilirubin  $< 2$ xULN, without hepatitis symptoms or rash, and who can be monitored weekly for 4 weeks, the following actions should be taken

- Notify the Novartis Medical Lead within 24 hours of learning of the abnormality to discuss subject safety.
- Continue study treatment
- Must return weekly for repeat liver chemistries (ALT, AST, alkaline phosphatase, bilirubin) until they resolve, stabilize or return to within baseline values
- If at any time these subjects meet the liver chemistry stopping criteria 1 - 5, proceed as described above
- If, after 4 weeks of monitoring, ALT  $< 3$ xULN and bilirubin  $< 2$ xULN, monitor subjects twice monthly until liver chemistries normalize or return to within baseline values.

Refer to Appendix 2 Liver Chemistry Monitoring, Interruption, Stopping and Follow-up Criteria for algorithm of liver chemistry monitoring, stopping and follow up criteria

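### Protocol Section 4.2.1 requires a permanent stop for subjects meeting the Section 5.10.2 liver criteria, while Section 5.10.2 tells that same group to stay on treatment

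*Protocol*

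**What the plan says.** Protocol Section 4.2.1 deals with liver chemistry twice. Its opening sentence ends treatment for unacceptable adverse events, "including meeting stopping criteria for liver chemistry defined in Section 5.10.1". It then opens a list with "In addition, study treatment must be permanently discontinued for any of the following reasons". One of the 11 bullets that follow is "Subject meets any of the liver chemistry threshold criteria (Section 5.10.2". The section closes off any return: "Once a subject has permanently discontinued from study treatment, the subject will not be allowed to be retreated".

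Section 5.10.1 sets out stopping criteria 1 to 5. Section 5.10.2 is headed as monitoring criteria. It describes subjects with ALT at least 3 but below 5 times ULN and bilirubin below 2 times ULN, "without hepatitis symptoms or rash, and who can be monitored weekly for 4 weeks, the following actions should be taken". The first action is "Notify the Novartis Medical Lead within 24 hours of learning of the abnormality to discuss subject safety" and the second is "Continue study treatment". Weekly repeat chemistries follow. The section's only route to a stop points back to Section 5.10.1: "If at any time these subjects meet the liver chemistry stopping criteria 1 - 5, proceed as described above".

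**The concern.** A subject who fits the Section 5.10.2 description gets opposite instructions from two current sections of the protocol. The Section 4.2.1 instruction is mandatory and cannot be undone within the study. Section 1.3.5 names hepatobiliary laboratory abnormalities as an identified risk of the drug, and collecting long-term safety data is part of the study's only objective.

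The same ALT result could therefore end treatment at one site and not at another. Where it did end treatment:

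- Section 8.4.4.3 requires an associated adverse event to be recorded.
- The subject then enters the SAP 2.7.1 summary of adverse events that led to stopping treatment and the SAP 2.3.1 table of end-of-treatment reasons.
- Exposure duration under SAP 2.4.1 is shorter.

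Where the site continued, none of this follows from that ALT result. Either course departs from one of the two sections, so a protocol-deviation listing alone cannot show which handling was off-protocol.

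**Working it through.** There is no planned figure to reproduce. The check is a comparison of text, followed by three short calculations.

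**1. Which subjects are affected.** Take a subject with ALT 4 times ULN, bilirubin 1 times ULN, no symptoms and weekly monitoring possible.

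| Provision | Applies at onset? | Instruction |
|---|---|---|
| 5.10.1 criterion 1 (ALT ≥3x ULN with bilirubin ≥2x ULN, or with INR >1.5 if measured) | No, taking INR as unmeasured or not above 1.5 | none |
| 5.10.1 criterion 2 (ALT ≥5x ULN) | No | none |
| 5.10.1 criterion 3 (ALT ≥3x ULN with symptoms) | No | none |
| 5.10.1 criterion 4 (ALT ≥3x ULN for ≥4 weeks) | Not yet | none |
| 5.10.1 criterion 5 (weekly monitoring not possible) | No | none |
| 5.10.2 | Yes | continue, with weekly chemistries |
| 4.2.1 liver bullet | Yes, through its reference to 5.10.2 | stop permanently |

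The last two rows conflict. For subjects who meet any of criteria 1 to 5, the opening sentence of 4.2.1 and Section 5.10.1 agree, so they are unaffected.

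**2. Consistency of the other liver text.** Criterion 4 presupposes subjects with ALT at or above 3 times ULN who are still on treatment. The reporting table in Section 8.4.7 has a separate row for this ALT and bilirubin range and allows for 4 weeks of monitoring. Sections 5.10.1, 5.10.2 and 8.4.7 are therefore consistent with one another. Read literally, the 4.2.1 bullet would leave criterion 4 no role for anyone who had entered 5.10.2 monitoring.

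**3. Scope.** The 4.2.1 list has 11 bullets and 1 is in conflict.

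**4. Timing.** Suppose ALT stays in the 5.10.2 range and no other criterion is met. Section 4.2.1 stops treatment at the first qualifying value; 5.10.2 leads to a stop through criterion 4 at 4 weeks. The difference is 4 × 7 = 28 days. With the SAP 2.1.1 divisor, 28 / 30.4375 = 0.92 months. If ALT falls below 3 times ULN instead, the difference is all of the subject's remaining treatment time, which the documents do not give.

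**5. Reporting.** SAP Section 1 gives 22 subjects in total. Cohort sizes are not stated, but none can exceed 22. One subject classified differently therefore moves a cohort percentage by at least 1/22 = 4.5 percentage points, and by more in a smaller cohort.

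**The case against.** The strongest reply is that this is a citation slip and not a second rule. Section 5.10.2 is headed as monitoring and does not use the word threshold, and the only stop it mentions is through criteria 1 to 5. The 4.2.1 list also repeats its opening sentence elsewhere: the bullet on adverse experiences largely restates the unacceptable adverse event clause. A repeated liver bullet with a wrong section number would fit that pattern. This is plausible and may explain the conflict. It does not cancel it: the opening sentence already cites 5.10.1, the bullets are introduced as additional reasons, and no visible text tells a site to disregard this one. Sections 4.2.2 and 5.4.1.3 both send the reader to 4.2.1 for when treatment ends.

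Second, each case should reach the sponsor within 24 hours, which makes divergence between sites less likely. That stands and reduces the practical risk, but it does not supply a single written rule.

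Third, the Appendix 2 algorithm might settle the matter. It is a figure absent from the text available for review, so this remains open.

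Fourth, with 22 subjects the planned listings of laboratory values, liver events, adverse events, disposition and exposure already allow a case-by-case reading. Much of this stands. What the SAP does not state is any output that links this laboratory group to whether treatment continued, so an added flag is useful but secondary.

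**Conclusion.** The concern holds. For one defined group, the liver bullet in Section 4.2.1 and Section 5.10.2 give opposite instructions, and the 4.2.1 instruction is irreversible. It should be fixed.

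The practical effect is limited. The study tests no hypotheses, affected subjects can be traced, and the documents do not show whether any of the 22 subjects entered the group. The 28-day figure assumes ALT persistently in range with no other stopping criterion met. The 4.5-point figure is a lower bound that uses only the total of 22. No event rate or cohort size is assumed. The conclusion rests on the visible text, without the Appendix 2 figure. Which clinical instruction should apply is for the sponsor to decide.

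**What to change.** **Protocol.** Reconcile the liver bullet in Section 4.2.1 with Sections 5.10.1 and 5.10.2, and check the Appendix 2 algorithm against the result, so that this group has one instruction. Since the last visit was on 23-Feb-2022, this serves the record and any reuse of the text. The cost is one bullet.

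**SAP or study report.** From the ALT and bilirubin data already collected, flag any subject who met the Section 5.10.2 laboratory definition, using the protocol's own limits. For each flagged subject, check symptoms and monitoring, and state whether treatment was continued or stopped. Add a footnote to the end-of-treatment reasons table and to the summary of adverse events that led to stopping treatment. If nobody met the definition, one sentence saying so is enough. The cost is one derived flag and one footnote in two outputs, with no new data and no effect on sample size.
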